6.5.7 Eastern Cooperative Oncology Group (ECOG)

ECOG scores and change from baseline will be summarized by visit using Safety Analysis Set.

6.6 PHARMACOKINETIC ANALYSES

6.6.1 Plasma Concentrations

Pharmacokinetic samples will be collected from patients in all cohorts at the following time points: predose (within 30 min prior to dose) and 2 hours (\pm 30 min) post-dose on both Day 1 and Day 15 (collection takes place in Cycle 1 for arm C). If pamiparib treatment is administered only for a 2-week (14-day) time period, PK samples will be collected on Day 1 and Day 14 instead. The time of study drug administration on the day prior to Day 15 (Day 14 for patients receiving only 2 weeks of pamiparib) must be recorded on the eCRF. Details concerning collection, handling, and processing of the PK plasma samples will be provided in the laboratory manual.

Plasma pamiparib concentration-time data will be summarized and displayed in both tabular and graphical form. Concentration-time data will be analyzed with standard noncompartmental and/or compartmental methods. Pharmacokinetic concentration data for pamiparib will be listed including the dose level, relative time to dosing, actual sample collection time. The concentration data will also be summarized with descriptive statistics for each time point by dose level. The number of patients with non-missing plasma concentration, mean, standard deviation, minimum, median, maximum, geometric coefficient of variation and geometric mean will be included in the summary.

7 INTERIM ANALYSIS

No interim analysis is planned.

8 CHANGES IN THE PROTOCOL PLANNED ANALYSIS

1. Sample size reduction: The overall sample size was reduced during the study since the expansion cohorts were considered too large for this non-randomized and non-registrational study.
2. All arm B expansion cohort related analysis and language are removed since it was decided not to enroll expansion cohort for arm B

3. Primary analysis will be performed on efficacy analysis set, not safety analysis set. No sensitivity analysis will be performed.

4. Exploratory objectives and endpoints in the protocol will not be explored in this SAP

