6 STATISTICAL METHODS

6.1 ANALYSIS POPULATIONS

Safety Analysis Set: includes all patients who received any dose of any of the study treatments (pamiparib, RT and/or TMZ). The Safety Analysis Set will be used for efficacy and safety analyses.

Efficacy Analysis Set: includes all patients in the Safety Analysis Set who:

Arms A & B: had a tumor assessment at baseline and at End of Treatment unless discontinued treatment or study early due to disease progression or death prior to tumor assessment.

Arm C: had measurable disease at baseline and at least one postbaseline tumor assessment unless discontinued treatment or study early due to disease progression or death prior to tumor assessment.

DLT-Evaluable Analysis Set: includes patients from escalation cohorts only in the Safety Analysis Set who received ≥ 42 Gy of RT (Arms A and B) and $\geq 70\%$ of scheduled pamiparib (Arms A, B and C) and TMZ (Arms B and C) during the DLT assessment window. All patients who had a DLT event will be considered DLT-evaluable regardless of study treatment intensity.

PK Analysis Set: includes all patients for whom valid pamiparib PK parameters can be estimated.

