6.2 DATA ANALYSIS GENERAL CONSIDERATIONS

6.2.1 Definitions and Computations

Study day: Study day will be calculated in reference to the first dose date of study drug. First dose date of study drug is defined as the earliest date of the first dose of any study drug. For maintenance phase, C1D1 is the first dose date. For assessments conducted on or after the first dose date, study day will be calculated as (assessment date – first dose date of study drug + 1). For assessments conducted before the first dose date, study day is calculated as (assessment date – first dose date of study drug). There is no study day 0.

In the situation where the event date is partial or missing, the date will appear partial or missing in the listings. Study day and any corresponding durations will be presented based on the imputations specified in [Appendix 1](#).

Baseline: Unless otherwise specified, a baseline value is defined as the last non-missing value collected before the time of first dose.

Treatment Duration:

Arm A&B regular treatment period (with RT) is defined as date of the last non-zero dose of latest treatment – first dose date of earliest treatment +1; treatment duration

Arm A&B maintenance period is defined as last non-zero dose of latest treatment in maintenance phase – date of C1D1 of maintenance phase +1

Arm C is defined as date of last non-zero dose of latest treatment – first dose date of earliest treatment +1.

RANO assessments:

ORR (objective response rate) is defined as proportion of patients with best overall response of CR or PR per RANO criteria (confirmed by a subsequent tumor assessment at least four weeks apart). Best overall response will be assessed from the start of study treatment until data cut-off date, disease progression or start of new anti-cancer therapy. Patients without postbaseline tumor assessment are considered non-responders.

Modified DCR (disease control rate) is defined as the proportion of patients with CR, PR or SD per RANO criteria as the response assessment at the end-of-treatment (EOT) visit, as

scheduled per protocol. Patients with no EOT tumor assessment, as scheduled per protocol (due to any reason), will be considered non-responders for modified DCR.

DCR (disease control rate) is defined as the proportion of patients with best overall response of CR, PR or SD per RANO criteria. CR or PR will be confirmed by a subsequent tumor assessment at least four weeks apart.

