6.4.1 Primary Efficacy Endpoints

Efficacy analysis will be performed on all patients for all arms. For Arm A and Arm C, phase 1b and phase 2 are presented in different table columns.

Arm A and Arm B

Modified Disease Control Rate is the primary efficacy endpoint in Arms A and B. It is defined as the proportion of patients with CR, PR or SD per RANO criteria as the response assessment at the end-of-treatment (EOT) visit, as scheduled per protocol. Patients with no EOT tumor assessment, as scheduled per protocol (due to any reason), will be considered non-responders for modified DCR. Modified DCR of Pamiparib combination therapy is assumed as 60% in the study population. The historical rate in a similar population is estimated as 40% (Rivera et al., 2010). No formal hypothesis testing will be performed. Two-sided binomial exact 80% and 95% CI of modified DCR will be constructed to assess the precision of the rate estimate.

Arm C

Objective Response Rate (ORR) is the primary efficacy endpoint in arm C. The analysis will be performed for the efficacy analysis set. It is defined as proportion of patients with best overall response of CR or PR per RANO criteria (confirmed by a subsequent tumor assessment at least four weeks apart). Best overall response will be assessed from the start of study treatment until data cut-off date, disease progression or start of new anti-cancer therapy. Patients without postbaseline tumor assessment is considered nonresponders. ORR of Pamiparib combination therapy is assumed as 25% in the study population. The historical rate in a similar population is

estimated as 10% (Chen et al, 2013). Two-sided binomial exact 80% and 95% CI of ORR will be constructed to assess the precision of the rate estimate.

In addition, the number (%) of the best overall response categories (CR, PR, SD, PD) will be presented.

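### The primary efficacy set drops treated patients whose required scan is missing for reasons other than progression or death, although the endpoint rules count them as non-responders; the all-treated rate and CI are no longer assured

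*SAP*

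**What the plan says.** **Protocol.** Section 11.2.1 assigns the Safety Analysis Set (all treated) to every efficacy analysis. Section 11.2.5.1 repeats this for modified DCR and gives the efficacy-evaluable set a sensitivity role only. For other endpoints, section 11.2.5.2 promises a sensitivity analysis of selected ones.

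**SAP, choice of set.** Section 8, item 3 reverses this: "Primary analysis will be performed on efficacy analysis set, not safety analysis set. No sensitivity analysis will be performed". It gives no reason. Other statements do not agree with it:

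- Section 6.1: "The Safety Analysis Set will be used for efficacy and safety analyses".
- Section 6.4.1, opening sentence: "Efficacy analysis will be performed on all patients for all arms".
- Section 6.4.1, Arm C: "The analysis will be performed for the efficacy analysis set".
- Section 6.4.1, Arms A and B: no set is named.

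**SAP, who is in the Efficacy Analysis Set (section 6.1).** Arms A and B: patients who "had a tumor assessment at baseline and at End of Treatment unless discontinued treatment or study early due to disease progression or death". Arm C: patients who "had measurable disease at baseline and at least one postbaseline tumor assessment unless discontinued treatment or study early due to disease progression or death".

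**SAP, missing scans.** For modified DCR (sections 6.2.1 and 6.4.1): "Patients with no EOT tumor assessment, as scheduled per protocol (due to any reason), will be considered non-responders for modified DCR". For ORR (section 6.2.1, repeated in 6.4.1): "Patients without postbaseline tumor assessment are considered non-responders".

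**The concern.** The endpoint rule and the set definition treat the same patient differently. Someone who stops for an adverse event, withdraws consent or is lost to follow-up, and has no scan, is a non-responder under the first and absent under the second. Once the Efficacy Analysis Set is primary, the non-responder rule can act on unscanned patients only if they stopped early for progression or death.

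The excluded patients could not have been responders under the SAP's own rule. Removing them leaves the numerator alone and shrinks the denominator, so the error can go only one way. The SAP reports the primary endpoints as a rate with exact 80% and 95% CIs and plans no formal test for Arms A and B, so that estimate and its CI are the primary result. The conflicting statements also leave the programmer to choose the primary denominator.

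**Working it through.** **Inputs**

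- Cohort sizes N: 40 (Arm A expansion) and 30 (Arm C expansion), SAP 5.
- Historical rates p0: 40% and 10%, SAP 5 and 6.4.1.
- CI: two-sided exact (Clopper-Pearson) 80% and 95%, SAP 6.4.1.
- m, the number of treated patients excluded for want of a scan: not in the documents. m = 0 to 4 is an assumption. Protocol 6.5.2 limits m by requiring an EOT visit within 7 days of stopping treatment. Protocol 6.7 foresees patients leaving without one.

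**The plan's own figures.** The exact lower bound for k responders of n at level c is the (1 − c)/2 quantile of Beta(k, n − k + 1).

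- Arm A, 80%: 20/40 gives 38.8% and 21/40 gives 41.2%, so 21 is the smallest count that excludes 40%. This matches SAP 5.
- Arm C, 80%: 5/30 gives 8.3% and 6/30 gives 10.9%, so 6 is the smallest count that excludes 10%. This matches SAP 5.

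Both benchmarks use the full cohort as denominator. They fit the all-treated set, and fit the Efficacy Analysis Set only if m = 0.

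**Effect of exclusions.** Set the true all-treated rate at p0. The m excluded are non-responders, so the remaining n = N − m respond with probability p0 × N/(N − m), which is the expected reported rate. For Arm A with m = 2: 0.40 × 40/38 = 42.1%. The count needed, k, is the smallest whose lower bound exceeds p0; the chance is P(X ≥ k) for X binomial with n = N − m and that probability.

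Arm A (N = 40, p0 = 40%):

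| m | Expected reported rate | 80% CI: k (chance) | 95% CI: k (chance) |
|---|---|---|---|
| 0 | 40.0% | 21 (7.4%) | 23 (1.9%) |
| 1 | 41.0% | 21 (7.3%) | 23 (1.8%) |
| 2 | 42.1% | 20 (12.5%) | 22 (3.6%) |
| 3 | 43.2% | 20 (12.3%) | 22 (3.5%) |
| 4 | 44.4% | 19 (20.1%) | 21 (6.6%) |

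Arm C (N = 30, p0 = 10%):

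| m | Expected reported rate | 80% CI: k (chance) | 95% CI: k (chance) |
|---|---|---|---|
| 0 | 10.0% | 6 (7.3%) | 8 (0.8%) |
| 1 | 10.3% | 6 (7.3%) | 7 (2.6%) |
| 2 | 10.7% | 6 (7.2%) | 7 (2.5%) |
| 3 | 11.1% | 6 (7.2%) | 7 (2.5%) |
| 4 | 11.5% | 6 (7.1%) | 7 (2.5%) |

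**The same responders, two denominators**

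- Arm A, 20 responders, m = 2: the 80% lower bound is 38.8% (20/40) or 41.1% (20/38).
- Arm A, 22 responders, m = 2: the 95% lower bound is 38.5% (22/40) or 40.8% (22/38).
- Arm C, 7 responders, m = 1: the 95% lower bound is 9.93% (7/30) or 10.30% (7/29).

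In each pair the interval includes the historical rate on all treated patients and excludes it on the reduced set. The effect is not uniform: m = 1 changes no Arm A count, and the Arm C 80% count falls to 5 only at m = 5 (5/25, lower bound 10.06%).

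**The case against.** **The change is disclosed, the study is descriptive, and the set keeps early progressors and deaths.** All true, and the last guards against the worst bias. Disclosure does not resolve the conflict with the non-responder rule, and with no test planned for Arms A and B the estimate and CI carry the result.

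**For Arm C the two rules can be read together**, with the non-responder rule meant for early progressors and deaths. That reading is possible, but the ORR rule in SAP 6.2.1 is unconditional.

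**In Arms A and B the non-responder rule might still apply to a patient scanned at an early EOT visit**, on the view that such a scan is off schedule. The protocol itself schedules that early visit, and the reading does nothing for patients with no scan.

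**A reader could recover the all-treated figures.** Counts, percentages and the cohort sizes of 40 and 30 give m and the all-treated rate, and an exact CI can be computed from those counts. But the plan does not report that CI. The disposition and deviation summaries (SAP 6.3.1 and 6.3.2) do not give the reasons for exclusion from the primary denominator.

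**PFS and OS stay on the Safety Analysis Set.** Correct, but they are secondary.

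**The size is hypothetical.** This stands. m may be 0, the shift at m = 1 is 1.0 point in Arm A and 0.3 in Arm C, and the SAP states no decision rule based on the CI excluding the historical rate.

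**Conclusion.** The concern holds and should be fixed. As written, the plan can only bias the primary rate and CI upward, it contradicts its own missing-scan rule, and it no longer assures the all-treated result that the protocol made primary. The bias is zero if nobody is excluded. For one to four exclusions the expected inflation is 1.0 to 4.4 percentage points in Arm A and 0.3 to 1.5 in Arm C; the count needed to exclude the historical rate falls at m = 2 in Arm A (80% and 95%) and at m = 1 in Arm C (95%).

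The conflict between the rules rests on the wording alone. The size rests on the assumed m and on true rates set equal to the historical ones. Comparison with 40% and 10% also supposes that those rates count all treated patients, which the documents do not say.

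**What to change.** In SAP 6.4.1, write:

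> The primary analysis of modified DCR uses the Safety Analysis Set. The primary analysis of Arm C ORR uses patients in the Safety Analysis Set with measurable disease at baseline. Patients without the required scan, for any reason, are non-responders and remain in the denominator. The Efficacy Analysis Set result is shown beside it as a sensitivity analysis, with the number excluded and the reasons, by arm.

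Replace section 8, item 3 to match. Align section 6.1, the opening sentence of 6.4.1, and section 6.4.2, which puts Arm C DCR and Arm A/B ORR on the Efficacy Analysis Set. The measurable-disease restriction for ORR follows protocol 11.2.5.2. The benchmarks 21/40 and 6/30 in SAP 5 then stand, the second provided all 30 Arm C expansion patients have measurable disease, as protocol 5.1 requires.

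The cost is SAP wording and one extra table column, with no new data. Reported rates may be slightly lower; if m = 0 in a cohort and all its patients have the disease status required, the two columns coincide.

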10 APPENDIX

Appendix 1. Imputation of Missing/Partially Missing Dates

Missing data will not be imputed unless otherwise specified. The imputation rule for the safety analyses will be used to address the issues with partial dates. When the start date or end date of an adverse event is partially missing, the date will be imputed to determine whether the adverse event is treatment emergent. When in doubt, the adverse event will be considered treatment emergent by default. The following rules will be applied to impute partial dates for adverse events:

Adverse Events

If start date of an adverse event is partially missing, impute as follows:

- If both month and day are missing and year = year of treatment start date, then set to treatment start date.
- If both month and day are missing and year \neq year of treatment start date, then set to January 01.
- If day is missing and month and year = month and year of treatment start date, the set to treatment start date.
- If day is missing and month and year \neq month and year of treatment start date, the set to first of the month.

- If start date is completely missing, set to treatment start date as long as adverse event end date is not before treatment start date.

If end date of an adverse event is partially missing, impute as follows:

- If both month and day are missing, then set to December 31.
- If only day is missing, then set to last day of the month.
- If end date is completely missing, do not impute.

Prior/Concomitant Medications, Disease and Medical History, Prior Therapy

When the start date or end date of a medication is partially missing, the date will be imputed to determine whether the medication is prior or concomitant. The following rules will be applied to impute partial dates for medications:

If start date of a medication is partially missing, impute as follows:

- If both month and day are missing, then set to January 01.
- If only day is missing, then set to the first of the month.

If end date of a medication is partially missing, impute as follows:

- If both month and day are missing, then set to December 31.
- If only day is missing, then set to last day of the month.

If start date or end date of a medication is completely missing, do not impute.

Death

In case complete death dates are not recorded, impute as follows:

- If both month and day are missing, then the imputed month and day will be 01Jan or the last date of the last date of patient known to be alive + 1, whichever is later.
- If only day is missing: If last known alive date is in same month as death date, then death date = last known alive date + 1; If death month is after last known alive date, then use first day of the month as death date.

New Anticancer Therapy

If the start day of a subsequent anticancer therapy is incomplete or missing, impute as follows:

- If both month and day are missing,

- 1) impute the date as 31Dec, if the year is earlier than the year of the first PD date + 1 or the treatment end date + 1, whichever is later.
 - 2) impute the date as 01Jan, if the year is later than the year of the first PD date or the treatment end date + 1, whichever is later.
 - 3) impute the date as the first PD date + 1 or the treatment end date + 1, whichever is later, if the year is the same year of first PD date + 1 or the treatment end date + 1, whichever is later.
- If only day is missing,
 - 1) impute the date as the first day of the month if year and month are available and partial new anticancer therapy date still could indicate it is at least one month later than the first PD date +1 or the treatment end date +1, whichever is later.
 - 2) impute the date as the last day of the month if year and month are available and partial new anticancer therapy date still could indicate it is at least one month earlier than the first PD date +1 or the treatment end date +1, whichever is later.
 - 3) impute the date as the first PD date +1 or the treatment end date +1, whichever is later, if the year and month are the same year and month of first PD date +1 or the treatment end date +1, whichever is later.
